1. SPECIFIC AIMS

The aims of this study are: 1) to determine the utility of fecal microbiota transplantation (FMT) in the treatment of patients with ulcerative colitis (UC) associated chronic antibiotic-dependent pouchitis (CADP) and chronic antibiotic refractory pouchitis (CARP) and 2) to study the changes in the microbial environment in patients with pouchitis (pre- and post-treatment) and 3) to assess the impact of therapy on the patient's perceived quality of life.

2. BACKGROUND AND RATIONALE

The spectrum of inflammatory bowel diseases (IBO) includes ulcerative colitis (UC) and Crohn's disease (CD). The etiology of these diseases is not clear but appears to involve aberrant immunological responses to intestinal bacteria in a genetically predisposed host. There is increasing evidence that the intestinal microbiota play an important role in the initiation and maintenance of IBO. Studies have demonstrated that the microbiota in patients with IBO differ from the healthy non-IBD individuals with a decrease in species such as *Clostridium leptum* and *Faecalibacterium prausnitzii*. This "dysbiosis" may result in fewer bacteria that produce short chain fatty acids which are important in protecting intestinal epithelium. The intestinal microbiota is important in maintaining homeostasis in the intestine and interacts with the host immune system to enhance immune function. Manipulation of the gut bacteria through the use of antibiotics, probiotics, and prebiotics have been shown to be beneficial in IBO. The use of antibiotics for the treatment of mild to moderate active FMT in UC-associated Pouchitis

Version 3.0, date finalized 06/26/2017

colonic Crohn's disease is effective in many cases. Antibiotics are often used to treat acute episodes of UC-associated pouchitis, an inflammatory condition seen in patients who undergo a restorative proctocolectomy with an ileal pouch anastomosis (IPAA). Probiotics (such as VSL-3) for the treatment of acute UC-associated pouchitis as well as for the secondary prevention of repeated episodes of pouchitis have been evaluated in several studies with positive results.

Greater than 50% of IBO patients who undergo an IPAA will develop pouchitis. Many of these patients will develop recurrent episodes of pouchitis and up to 5% will develop chronic pouchitis requiring maintenance therapy with antibiotics or other agents and may even pouch excision. The etiology of pouchitis is unknown, but theories include fecal stasis leading to bacterial overgrowth and alteration of normal commensal flora in a genetically susceptible individual. Microbiome studies in UC pouch patients have shown alterations in the fecal flora with increases in anaerobic bacteria and sulfate producing bacteria.

In a recent study, pouch microbiomal environments appeared to be distinctly unique in patients with a normal UC-associated IPAA and those with UC-associated pouchitis (Zelia GC, IBD, May 2011). Pouchitis samples showed more *Clostridium* and *Eubacterium* genera compared to healthy UC pouch patients. The current treatment approaches for pouchitis are based on small randomized controlled trials showing some efficacy with use of antibiotics and probiotics. However, the choice of antibiotics, dose, and duration of treatment are largely empiric. In addition, probiotics have limited durability after discontinuation, while the antibiotics most utilized have known side effects as well as the potential for selecting multi-drug resistant bacteria. Development and study of additional therapeutic options for pouchitis treatment are areas for further research.

Fecal microbiota transplantation (FMT) has been shown safe and effective as a method of manipulating the microbiota in patients with recurrent *Clostridium difficile* infection (van Nood et al. NEJM 2013). In the literature, there are 41 cases in 17 articles reported of fecal transplantation in the treatment of inflammatory bowel disease (IBD). The majority experienced a reduction of symptoms (19/25), cessation of IBD medications (13/17), or disease remission (15/24) (Anderson, Edney et al. APT 2012). Some of the weaknesses of the available data are small number of cases, unreported or not clearly defined IBD characteristics, and lack of uniformity when measuring outcome variables. A recent prospective controlled pilot trial of use of FMT for chronic refractory pouchitis revealed negative outcomes. However, the researchers used a single dose and administered the stool preparation through a nasogastric tube. Several studies have shown lower success rates of FMT in *C. difficile* with use of nasofeeding tube versus a colonoscopy or sigmoidoscopy. In addition, a recent trial of use of FMT to treat ulcerative colitis showed improvement in clinical activity scores when five successive fecal enemas were used (Kunde 2013). At the present, it is unclear which phenotype of IBD-ulcerative colitis, Crohn's disease, or pouchitis or what level of disease activity is best treated with fecal

FMT in UC-associated Pouchitis

Version 3.0, date finalized 06/26/2017

microbiota transplantation.

3. STUDY DESIGN

The primary investigative design will be a single arm study to determine if FMT has the potential to be used in the treatment of chronic pouchitis.

3.1 *Study Objectives:*

Primary Objective: To determine the safety and tolerability of fecal microbiota transplant (FMT) in treatment of chronic pouchitis

Secondary Objective: To study the microbial environment of IPAA/UC associated pouches in patients presenting with symptoms of pouchitis with and without endoscopy-visualized pouchitis and to assess the impact of the therapy on the patient's perceived quality of life

3.2 *Study design Type/Phase:* This is a two center, Phase 1 open label study designed to determine the safety, tolerability and use of fecal transplant in patients with pouchitis and to study the differences in microbiome in patients before and after treatment with FMT.

3.3 *Sites Centers of Research:* This study will be conducted in the Emory Clinic- Adult Digestive Disease Clinic and Colorectal Surgery Clinic, the Emory Center Endoscopy Center, and St. Joseph's Hospital (SJH) in Atlanta, GA.

3.4 *Measures to minimize/avoid bias:* Eligible subjects will be given options of other treatments if they choose not to participate.

3.5 *Study duration:* The total duration of the study for each patient will be twelve weeks.

3.6 *Study Procedures*

The following protocol essentially requires two sets of study procedures. One set of study procedures outlines testing requirements for the donor of allogenic human feces (see **Table 1.** Donor Related Study Activities). The other set outlines activities and expectations of the research participant who will receive the donated stool specimen (see **Table 2.** Research Participant Study Activities). The donor set of activities will be managed by [name], a sub-investigator and Associate Professor of Medicine within the Division of Infectious Diseases. In the past, [name] has overseen the donor recruitment and screening within previous FMT trials via ordering the appropriate antibody screens, fecal sample preparation (e.g. use of saline, etc.) and any other necessary tests to ensure that the fecal specimen is non-infectious and safe for insertion into research participants. [name] still oversees this process and prepares the allogenic human fecal FMT in UC-associated Pouchitis

Version 3.0, date finalized 06/26/2017

donation in her lab on site. However, she will not be able to provide these activities listed in **Table 1** for effort.

All activities outlined in **Table 1** would be billed to the sponsor to compensate [name] for her time and effort to support our participants and overall project goals and needs. The donor related activities will take place before the research participant is seen for informed consent during the screening visit (see **Table 2**). This is done to ensure that the donor has been screened for infectious diseases in a timely manner and that [name] has ample time to prepare the allogenic human fecal specimen in her lab for the transplant on the enrollment visit. Donors will be screened every four weeks which is standard protocol for [name] lab. More details about the donor screening process and requirements are listed in the protocol section **3.6 a) Donor Stool Collection and Processing**.

Table 1. Donor Related Study Activities

Donor Activity	Specific Test Ordered	Visit
Blood/Serology Testing	
 1. Hepatitis A IgM and IgG 2. Hepatitis B S Ab/Sag/Core Ab 3. Hepatitis C Ab 4. RPR 5. Human Immunodeficiency Virus (HIV) 1 and 2 Antibody 	Donor Screening (every four weeks)
Stool Testing	
 1. Clostridium Difficile PCR 2. Salmonella, Shigella, and Campylobacter 3. Ova and parasites 4. H. Pylori antigen 5. 5.Vancomycin resistant Enterococcus (VRE) 6. Carbapenemase resistant Enterobacteriaceae 	
Fecal Sample Preparation for Donation ¹	N/A	

¹The fecal sample will be prepared for the FMT in [name] laboratory on site. Please refer to section 3.6 a for more detailed information regarding the donor fecal sample processing activities.

Table 2 outlines a total of five complete research visits for each research participant: screening (initial), enrollment (transplant), 2 weeks post-transplant (may be a phone call at the discretion of the physician), 4 weeks post-transplant, and 3 months post-transplant. For the initial or screening visit, research participants will first complete the informed consent process with a member of the research team. Upon completion of the informed consent process, the participant will receive phlebotomy to collect blood for plasma chemistries, CBC with differential, and platelet counts.

Urine will also be collected and screened for basic urinalysis. Women of child bearing potential

(WOCBP) will be screened using urine pregnancy kits to test for beta HCG levels. These kits will be provided by the sponsor. The results of these kits will be used as the final determination of pregnancy for WOCBP. WOCBP who screen positive for beta HCG (i.e. are pregnant) will be excluded from the study for the safety of both the mother and her unborn child. Phlebotomy for plasma collection, eventual CBC with differential, and platelet count will be performed for each research visit. Urine and stool will also be collected for each study visit. In addition to phlebotomy, urine collection, and stool collection, research participants will also receive a physical exam for each research visit.

Waist and hip circumference will be measured during the screening visit only. For the second visit (i.e. enrollment), the research participant will also receive a physical exam along with a flexible sigmoidoscopy. The flex sigmoidoscopy will be performed under moderate sedation using propofol per usual anesthesia services. The flexible sigmoidoscopy will be used to gain access to the pouch and to take a mucosal tissue pouch biopsy.

Table 2. Research Participant Study Activities

Visit Procedures	Screening²	Enrollment	2 Week³ (+/- 3 days)	4 weeks (+/- 7 days)	3months (+/- 14 days)
Informed Consent Process	X				
Physical Exam	X	X	X	X	X
Urine pregnancy testing for WOCBP	X				
Phlebotomy	X	X	X	X	X
Labs and Specimen Processing:					
Stool collection	X	X	X	X	X
Plasma collection	X	X	X	X	X
Urine collection	X	X	X	X	X
CBC w/diff., platelet count ⁴	X	X	X	X	X
Flexible Sigmoidoscopy with Moderate Sedation		X			
Mucosal Biopsy Collection		X			
Waist and hip circumference measures	X				
Fecal Microbiota Transplant		X			

Modified PDAI	X (clinical)	X	X (clinical)	X(clinical)	X (clinical)
Quality of Life Questionnaires	X			X	X
Food Recall Questionnaire		X		X	X

²If both screening and enrollment visits occur within 7 days, research samples may not be recollected at the enrollment visit, at the discretion of the investigator

³The 2-week visit may be conducted over the telephone for subjects who live a significant distance from the study site and at the discretion of the study investigator. Biological samples will not be collected on subjects who complete visit via telephone, however subject may be asked to mail in a stool sample for testing

⁴ Screening labs for hemoglobin (Hgb), platelet count, and absolute neutrophil count (ANC) may be performed within six months of screening visit

3.6. a) Donor Stool Collection and Processing

The standard donor stool will be obtained from a donor who has undergone testing for potential transmittable infections. These include Hepatitis A, Hepatitis B, Hepatitis C, syphilis, HIV, *H pylori*, *Salmonella*, *Shigella*, *Campylobacter*, *C. difficile*, as well as screening for ova and parasites, and multidrug resistant organisms (specifically carbapenemase-producing *Enterobacteriaceae* and vancomycin-resistant *Enterococcus*). This testing is performed through Emory Medical Laboratories. In addition, the donor will be screened for illnesses that would exclude him from donating stool for the current study (see attached screening questionnaire). Donor screening will be completed and all results confirmed negative prior to use of donor stool for transplant. Standard donors will be re-screened every six months.

The standard donor voids the stool at home just prior to leaving for work in the morning. The stool is dropped off in the microbiology laboratory within 60 minutes of being voided. The stool is processed within 60 minutes of the drop off, and administered within 120 minutes of the processing. The time that elapses from the stool being voided by the donor and administered to the patient ranges from 60-240 minutes. Donor stool will be handled as a level 2 biohazard with appropriate universal precautions.

Appropriate Personal Protective Equipment (PPE) will be worn by personnel while handling/processing donor fecal material:

- Nitrile gloves will be worn while working with all potentially infectious agents. Gloves should be removed before touching common objects in public areas. Hand washing will be performed each time gloves are changed.
- Gloves should be removed prior to removal of other PPE. Gloves should be removed before leaving the laboratory.
- Lab coats will be worn over clothing while handling/processing stool specimen and preparing FMT solution

FMT in UC-associated Pouchitis

Version 3.0, date finalized 06/26/2017

- Contaminated clothing will be decontaminated and laundered on-site or by a commercial laundry service.
- Protective eyewear/goggles will be used, if splash potential exists
- Laboratory access will be limited to authorized personnel only.
- Biohazard containers for disposal of contaminated materials are readily accessible in the processing area.
- Good laboratory techniques will be exercised to minimize the formation of aerosols, droplets, spatters, splashes.

The FMT processing (performed by [name]) involves taking of the standard donor's stool which is received in the clinical microbiology laboratory along with a short questionnaire (see Appendix 2). The hood is terminally cleaned with 10% sodium hypochlorite followed by 70% ethanol. The hood area is then lined with clean lab mats. Thirty cubic centimeter (ccs) saline aliquots are poured into 50 ml centrifuge tubes and 1 cm³ of stool is distributed in these aliquot containers. The stool is mixed gently using a tongue depressor until a smooth suspension is formed. The contents are then filtered using a standard Parapak filter. The suspension is allowed to settle in the 50-ml centrifuge tube for 10 minutes and then poured off into a sterile container. This filtrate is then drawn up in 60 cc syringes, and labeled "For Enteral Use Only". Syringes are placed into sealed biohazard labeled bags for transport.

3.6. b) Fecal Microbiota Transplant (FMT) Procedure

Subjects will be asked to clean out their pouch using two over the counter enemas no longer than 3 hours before the procedure time. This is standard of care for patients undergoing routine flexible sigmoidoscopy. Subjects will also be asked to take 4 mg of loperamide (over-the-counter anti-diarrheal medication) one half hour before the FMT.

Subjects will be placed in the left lateral decubitus position with elevated hips in a designated private room in clinic or endoscopy suite for 90 minutes of FMT intervention. Subjects will be asked to rotate 180 degrees slowly during a 10-minute period. Subjects will be monitored for 30 minutes after FMT for any adverse events and discharged.

Concomitant Medications: Permitted concomitant medications: Patients may remain on chronic medications during the study period.

Prohibited medications: Patients will need to be off antibiotics and probiotics for at least 48 hours prior to fecal transplant.

End of the study: The end of study for each patient is defined as the date of the last visit (i.e. 3 month visit post-transplant).

Timeline: All the proposed aims and enrollments will be carried out within 24-month period. We do anticipate a large proportion of eligible subjects may travel to Emory as the interest in this therapeutic platform is quite high with us already receiving numerous requests.

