3.7 Inclusion and Exclusion criteria

The following lists outline key criteria used by the principal investigator, sub-investigators, and study team to determine who can and cannot be in this study.

Inclusion Criteria

1. Males and females between the ages of 18 and 80 (inclusive) with ulcerative colitis-associated IPAA with and without pouchitis
2. Eligible patients will be identified through the Emory Clinic (TEC), St. Joseph's Hospital (SJH), and Emory University Hospital (EUH)
3. Signed informed consent

Exclusion Criteria

1. Age <18 years or >80 years of age
2. Exposure to immunosuppressive therapy within the 4 weeks prior to enrollment or their expected use within 1 month of FMT
3. Concomitant *Clostridium difficile* infection
4. Suspected Crohn's disease
5. Documented active infection of any kind
6. Patients on anti-coagulant therapy, with platelet count less than 50,000, significant anemia with hemoglobin < 7, or those with other conditions that place them at increased risk of bleeding
7. Pregnant or breastfeeding women (pregnancy will be verified using urine pregnancy kits)
8. Need for imminent surgery
9. Absolute neutrophil count (ANC) < 1000 or history of opportunistic infection
10. Administration of any investigational drug within one month before FMT

Demographic data, including prior history of pouchitis with sub-classification into chronic antibiotic resistant (refractory) pouchitis, chronic antibiotic use as well as previous treatments will be recorded. Measures of waist and hip circumference and waist to hip ratio will be calculated and recorded. Stool samples, urine, and serum samples will be collected. Patients will be screened at entry for enteric pathogens (*C. difficile*, routine bacterial stool culture, ova and parasites) and positive results will exclude entry to the study.

Fecal samples from subjects will be analyzed for microbiome genetics, and metabolomic profiles before and four weeks after therapy. Scored symptoms according to the modified pouch disease activity index (mPDAI) (**Appendix 1**) as proposed by Shen et al. will also be recorded.

FMT in UC-associated Pouchitis
Version 3.0, date finalized 06/26/2017

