4. BIOLOGICAL SPECIMENS TO BE ACQUIRED

1. *Fecal sample*- The patient will submit a stool specimen in a container for genomic analysis at week 0, week 2, week 4, and week 12. Prior to enrollment, the patients will undergo PCR testing for *C. difficile*, routine stool culture, and ova and parasites. Any remaining stool sample will be used for research purposes for microbiota evaluation by 16S sequencing.
2. *Mucosal Pouch Tissue* -A total of up to 6 mucosal biopsies will be taken during routine standard of care flexible sigmoidoscopy procedure in patients undergoing investigation for presumed pouchitis or for routine surveillance of the pouch in patients without pouchitis. Two to four will be sent to pathology for assessment of histology. Two to four biopsies will be obtained for research purposes. No more than a total of 6 will be taken. All non-research biopsies will be placed in saline and transported to the Pathology Department at Emory immediately. Research related

biopsies will be collected by the study team and transported to the Pathology Department at Emory University.

3. *Stool*- Additional stool will be collected after treatment 4 weeks and 3 months after fecal microbial transplant (FMT). If the first and second study visit occur within 48hours, the second collection of biologic samples will be at the discretion of the study doctor.

Samples collected through this study will be given a de-identified code that is not derived from or related to information about the individual and is not otherwise capable of being translated to identify an individual. The samples will then be barcoded and transported to a central core laboratory at Emory University managed by [name]. Fecal and mucosal samples will be saved and stored in locked refrigerators/freezers in [name] laboratory in the Woodruff Memorial Building. DNA will be extracted for sequencing at this laboratory using automated extraction. Sequencing of the 16S regions will be performed in [name] laboratory.

Plasma and urine samples will be collected from each patient at study visits as illustrated in the study procedures table, and will be barcoded and saved in locked freezers in [name] laboratory in the Woodruff Memorial Building until all the samples are collected. At such time, they will be transported to [name] laboratory in the Whitehead building for metabolomic profiling.

Biological samples will not be collected on subjects who complete study visits via telephone follow-up.

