7.1 Women of Childbearing Potential (WOCBP)

Pregnant or nursing (lactating) women, where pregnancy is defined as the state of a female after conception and until the termination of gestation, confirmed by a positive serum human chorionic gonadotrophin laboratory test (>5 miU/mL) will be excluded from participation in this study.

Women of child-bearing potential, defined as all women physiologically capable of becoming pregnant, including women whose career, lifestyle, or sexual orientation precludes intercourse with a male partner and women whose partners have been sterilized by vasectomy or other means must agree to use two birth control methods throughout their participation in the study. The two methods can be a double barrier method or a barrier method plus a hormonal method.

Subjects will be counseled by the study team regarding adequate forms of contraception.

- Adequate barrier methods of contraception include: diaphragm, condom (by the partner), intrauterine device (copper or hormonal), sponge or spermicide. Hormonal contraceptives include any marketed contraceptive agent that includes an estrogen and/or a progestational agent.
- Reliable contraception should be maintained throughout the study.

Women are considered post-menopausal and not of child bearing potential if they have had 12 months of natural (spontaneous) amenorrhea with an appropriate clinical profile (e.g. age appropriate, history of vasomotor symptoms) or six months of spontaneous amenorrhea with serum FSH levels > 40 mIU/mL and estradiol < 20 pg/mL] or have had surgical bilateral oophorectomy (with or without hysterectomy) at least six weeks prior to study enrollment. In the case of oophorectomy alone, only when the reproductive status of the woman has been confirmed by follow up hormone level assessment is she considered not of child bearing potential.

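### Table 2 schedules the pregnancy test at screening only, although sedation and FMT take place at a later visit with no stated maximum interval

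*Combined protocol and SAP*

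**What the plan says.** **Pregnancy.** In the combined protocol and SAP, Section 3.6, Table 2, the row "Urine pregnancy testing for WOCBP" has one mark, under Screening. The text before the table says of the urine kits: "The results of these kits will be used as the final determination of pregnancy for WOCBP". Exclusion 7 in Section 3.7 also relies on the urine kits. Section 7.1 differs: it describes pregnancy as "confirmed by a positive serum human chorionic gonadotrophin laboratory test", and Table 2 has no row for a serum test. Section 7.1 adds that women of childbearing potential "must agree to use two birth control methods throughout their participation in the study".

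**Timing of FMT.** Section 3.6 lists screening and enrollment as separate visits and places the transplant at enrollment. Table 2 puts the sigmoidoscopy, sedation, biopsy and FMT in that column.

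**Enteric pathogens in recipients.** Section 3.7 says "Patients will be screened at entry for enteric pathogens", and a positive result bars entry. Section 4, item 1 says "Prior to enrollment, the patients will undergo PCR testing for" *C. difficile*, together with stool culture and ova and parasites. Table 2 has no row for these tests.

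**The concern.** The pregnancy exclusion is there to protect the mother and the fetus from what happens at the enrollment visit. Its only scheduled test belongs to a different visit, and the plan does not say how old the result may be when sedation and FMT begin. A woman who conceives after screening, or whose pregnancy is too early to show in urine at screening, could reach the procedure without anyone knowing.

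The enteric-pathogen results raise a similar but weaker question, because their age at FMT is also unstated. This bears on the analysis as well as on safety. The primary endpoint in Section 10 rests on symptoms alone, and an enteric infection can produce some of the same symptoms.

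**Working it through.** The plan gives no figure to reproduce here. The check is whether any section limits the time from test to FMT, or schedules a second test.

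1. **Table 2, footnote 2 (7 days).** If screening and enrollment fall within 7 days, research samples need not be recollected. This governs recollection and does not limit the gap.
2. **Section 4, item 3 (48 hours).** If the first two visits fall within 48 hours, a second collection is left to the study doctor. This too governs recollection only, and it disagrees with the 7 days in footnote 2.
3. **Table 2, footnote 4 (six months).** Screening hemoglobin, platelet count and neutrophil count may date from within six months of the screening visit. This is the only age limit on a recipient eligibility test. It does not cover pregnancy or enteric pathogens, and it is counted from screening, not from FMT.
4. **Section 3.5 (twelve weeks per patient).** Could this imply a screening window? Twelve weeks is 84 days. Table 2 places the last visit 3 months after transplant, ±14 days, and Sections 3.7 and 4 call it week 12.
   - Last visit at day 84: 84 − 84 = 0 days left for screening; at its earliest, 84 − (84 − 14) = 14 days.
   - Last visit at day 91 (13 weeks): 84 − 91 = −7 days; at its earliest, 84 − (91 − 14) = 7 days.

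   Follow-up uses up the twelve weeks, so this sentence cannot serve as a screening window.
5. **Section 9.** The procedure is to take place at the follow-up visit after consent. No interval is given.
6. **Samples at enrollment.** Table 2 marks urine and stool collection at enrollment, but no pregnancy test. Section 4 assigns the week 0 stool to genomic analysis and mentions no repeat PCR.

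No section supplies a maximum interval or a second pregnancy test.

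**Bearing on the endpoint.** In Appendix 1 the clinical component has a maximum of 2 (stool frequency) + 1 (bleeding) + 2 (urgency or cramps) + 1 (fever) = 6 points. Stool frequency, urgency or cramps, and fever account for 2 + 2 + 1 = 5 of the 6, and an enteric infection can raise all three. One misclassified participant moves the response rate by 1/11 = 9.1 percentage points. That holds for any misclassification in a trial of 11 and says nothing about how often this one would occur. The documents give no *C. difficile* rate from which to estimate that.

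**The case against.** The best defense is that the exclusions are not limited to status at screening. Exclusion 3 bars concomitant *C. difficile* infection and exclusion 7 bars pregnancy, and both still apply on the day of FMT. This stands. A reader might infer that a woman who conceives after screening meets every rule and is properly transplanted, but the text does not support that. She still meets an exclusion; what is missing is a scheduled test that would reveal it.

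The contraception requirement in Section 7.1 is a real safeguard. It lowers the probability of pregnancy but does not update the test result.

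The gap may also be short. Footnote 2 and Section 4 both provide for visits close together, in which case a second test adds little. A reader might infer from footnote 2 that gaps of weeks or months are expected. It is a conditional sentence that allows for longer gaps without predicting them.

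On *C. difficile*, testing is set before enrollment, which is the transplant visit, so it is not tied to the screening visit and a site could test shortly before FMT. Only the maximum age is missing. A reader might also infer a bias towards success from Section 2, where "Fecal microbiota transplantation (FMT) has been shown safe and effective as a method of manipulating the microbiota in patients with recurrent" *C. difficile* infection. That statement concerns recurrent infection, whereas the case here is an infection missed at baseline. If the infection cleared after FMT, the participant could be counted as a responder; if it persisted, as a non-responder or a relapse. Section 3.7 also describes both patient categories as having histologic pouchitis, so clearing an infection need not resolve the symptoms. The direction is not established.

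**Conclusion.** The pregnancy point holds. The only scheduled test is at screening, FMT under sedation is at a later visit, and the interval is unlimited on paper. The flaw is a gap in detection; the exclusion itself remains in force. The residual risk cannot be quantified, since the documents give neither the number of women of childbearing potential nor the expected interval, and contraception reduces it. A repeat test is justified because it is cheap and specific. It would not remove the risk entirely, because a very early pregnancy can also be missed at enrollment.

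The conflict between the urine kit as final and a serum test as confirmation is a separate inconsistency on the same exclusion.

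The enteric-pathogen point is secondary. The age of the results at FMT is unstated, and an undetected infection could misclassify the symptom-only endpoint in either direction, by an amount the documents do not allow to be estimated.

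**What to change.** - In Table 2, mark the urine pregnancy test in the Enrollment column as well, to be read before sedation, and bring the Section 3.6 text into line.
- Reconcile Section 3.6 and exclusion 7 (urine kit) with Section 7.1 (serum confirmation), so that one determination of pregnancy is stated throughout.
- Add a Table 2 row for recipient enteric-pathogen testing, and state the maximum age of those results at FMT and what follows if it is exceeded. The interval is for the sponsor to set.
- Reconcile the 7-day and 48-hour recollection rules, since they decide whether urine is collected at enrollment at all.

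The cost is a protocol amendment and at most 11 further kits, one per participant if all were women of childbearing potential, of a type that Section 14.2 already charges to the sponsor. A urine sample would also be needed where footnote 2 would otherwise waive recollection, and a visit may occasionally be delayed. Repeat stool tests would be needed only where results exceed the age the sponsor sets.
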